### 5.2.12 Vital Signs

Temperatures reported in Fahrenheit will be converted to Celsius for reporting using the following formula:

$$\text{Celsius} = (\text{Fahrenheit} - 32)/1.8$$

The converted values will be set to one decimal.

### 5.2.13 Physical Examination

If the CRF field ‘Were there any abnormalities in the physical examination’ in the physical examination form is answered ‘No’ in a given visit, then all the body systems will be reported as ‘Normal’ for that visit for the summary purpose.

### 5.2.14 Inexact Values

In the case where a variable is recorded as “ $> x$ ”, “ $\geq x$ ”, “ $< x$ ” or “ $\leq x$ ”, a value of x will be taken for analysis purposes, unless specified otherwise. In the listing, data will be reported as collected.

For example, for lab values that are entered as “ $<0.3$ ” or “ $>1476$ ”, this rule means that for summary tables, 0.3 or 1476 will be used. In the lab listings the original values (“ $<0.3$ ” or “ $>1476$ ”) will be displayed.

### 5.2.15 Clinical Dementia Rating Scale – Sum of Boxes (CDR-SB)

The CDR-SB is a tool that measures the severity of cognitive impairment and dementia in six domains: memory, orientation, judgment and problem solving, community affairs, home and hobbies, and personal care. The CDR-SB score is calculated by adding up the scores of each domain, which range from 0 (normal) to 3 (severe impairment). The total CDR-SB score can range from 0 to 18, with higher scores indicating more severe dementia.

QMD Ref: Worldwide-TMP-ST-054-1.0_Effective: 12Aug2022	Governing QMD: Worldwide-SOP-ST-026
Confidentiality Statement	
This document is the property of Worldwide Clinical Trials Inc. and may not be duplicated, copied, altered or removed from company without prior approval from Worldwide Quality Assurance or in compliance with Worldwide Standard Operating Procedures.	

Worldwide Clinical Trials Controlled Quality Management Document		
 WORLDWIDE CLINICAL TRIALS	Sponsor:	EIP Pharma, Inc.
	Protocol Number:	EIP21-NFD-504
STATISTICAL ANALYSIS PLAN		

## 5.2.16 Neuropsychological Test Battery Composite Scores

To compute each of the composite scores defined below, it is necessary first to standardize the performance scores from each of the component cognitive tests at each of the post-baseline visits using data from the study baseline.

For each subject, for each visit the composite score is obtained by averaging the standardized change from baseline scores for the relevant cognitive tests. The details of cognitive tests are provided in Appendix A.

*Table 3: Composite Scores of the Neuropsychological Test Battery Used in the Study*

Composite score	Tests included in composite
NTB	DET, IDN, OCL, ONB (accuracy only)
Attention	DET, IDN

The NTB composite score is a secondary endpoint, while the Attention composite is an exploratory endpoint.

A comparison of individual scores to baseline data will be conducted. The process will be as follows:

- Performance on each Cogstate test will be standardized relative to baseline data (i.e., the score will be converted to a z-score by subtracting the study sample's mean at baseline from the score and dividing by the standard deviation (SD) of the study sample's baseline).
- The multiplicand equals 1 for tests for which a higher score is indicative of better cognitive performance (i.e., OCL, ONB (Accuracy)) and -1 for tests where a lower score is indicative of better cognitive performance (i.e., DET, IDN).

The z-score will be calculated as follows:

$$z - Score(z_{ijt}) = \frac{(x_{ijt} - \bar{x}_{1t})}{\sigma_{1t}} \times \text{Multiplicand}$$

Where:

$t$  = is the test indicator

$i$  = indexes subject  $i$

$j$  = indexes the assessment at the  $j^{\text{th}}$  visit for subject  $i$  ( $j = 1$  means baseline)

$x$  = cognitive score

$\bar{x}_{1t}$  = mean performance score of the study sample for test  $t$  at baseline

QMD Ref: Worldwide-TMP-ST-054-1.0_Effective: 12Aug2022	Governing QMD: Worldwide-SOP-ST-026
Confidentiality Statement	
This document is the property of Worldwide Clinical Trials Inc. and may not be duplicated, copied, altered or removed from company without prior approval from Worldwide Quality Assurance or in compliance with Worldwide Standard Operating Procedures.	

Worldwide Clinical Trials Controlled Quality Management Document		
 WORLDWIDE CLINICAL TRIALS	Sponsor:	EIP Pharma, Inc.
	Protocol Number:	EIP21-NFD-504
STATISTICAL ANALYSIS PLAN		

$\sigma_{I,t}$  = Standard Deviation of the study sample for test  $t$  at baseline

Each of the composite scores described above will be calculated as follows:

1. For a given subject at a given assessment, determine if as many valid test scores are available as specified in table above.
2. If the condition in Step 1 is not satisfied, set the composite to missing for that assessment. If the condition in Step 1 is satisfied, proceed with the following steps:
3. Compute z-scores (based on the formula provided above) using the score for the primary outcome measure listed in Appendix A (Section 11) for each available test included in the corresponding Composite (listed in *Table 3*).
4. Calculate the mean of the z-scores to compute the Composite score for a given subject at a given assessment.

### 5.2.17 Alzheimer's Disease Cooperative Study – Clinical Global Impression of Change (ADCS-CGIC)

The ADCS-CGIC rating is made on a 7-point scale similar to other global change scales, where a lower score indicated marked improvement. No imputation of missing scores will be done.

0	Not Assessed
1	Marked Improvement
2	Moderate Improvement
3	Minimal Improvement
4	No Change
5	Minimal Worsening
6	Moderate Worsening
7	Marked Worsening

### 5.2.18 Dementia Cognitive Fluctuations Scale (DCFS)

The DCFS consists of 4 items with each item based on 5-point Likert Scale. The total score (ranging from 4 to 20) is calculated as sum of each item score (ranging from 1 to 5) with higher score indicating more severe CFs. No imputation of missing scores will be done.

Difference in function	5	A very large difference (a very severe impact on daily functioning)
	4	A large difference (a severe impact on daily functioning)
	3	A moderate difference (a clear impact on daily functioning)
	2	A slight difference (only a mild impact on daily functioning)
	1	No difference (no impact on daily functioning)

#### Confidentiality Statement

This document is the property of Worldwide Clinical Trials Inc. and may not be duplicated, copied, altered or removed from company without prior approval from Worldwide Quality Assurance or in compliance with Worldwide Standard Operating Procedures.

Worldwide Clinical Trials Controlled Quality Management Document		
 WORLDWIDE CLINICAL TRIALS	Sponsor:	EIP Pharma, Inc.
	Protocol Number:	EIP21-NFD-504
STATISTICAL ANALYSIS PLAN		

Daytime sleep	5	3 hours or more
	4	2 hours to 3 hours
	3	1 hour to 2 hours
	2	Less than 1 hour
	1	Not at all
Daytime drowsiness	5	3 hours or more
	4	2 hours to 3 hours
	3	1 hour to 2 hours
	2	Less than 1 hour
	1	Not at all
Level of consciousness	5	Mostly asleep
	4	Drowsy, but difficult to arouse
	3	Drowsy, but moderately easy to arouse
	2	Drowsy, but easy to arouse
	1	Mostly alert

## 5.2.19 Neuropsychiatric Inventory (NPI-12)

The Neuropsychiatric Inventory (NPI-12) assesses twelve behavioral domains common in dementia and is administered to the caregiver. Ten behavioral domains and 2 neurovegetative items are included in the NPI-12. The domains are as follows: delusions, hallucinations, agitation/aggression, depression/dysphoria, anxiety, elation/euphoria, apathy/indifference, disinhibition, irritability/lability, aberrant motor behavior, sleep, and appetite and eating change. Each domain is rated in 3 scores as below:

- Frequency with 4 response options ranging from 1 (Occasionally) to 4 (Very Frequently)
- Severity with 3 response options ranging from 1 (Mild) to 3 (Severe)
- Distress with 5 response options ranging from 0 (No distress) to 5 (Very Severe or Extreme)

Frequency	
1	Occasionally - less than once per week
2	Often - about once per week
3	Frequently - several times per week but less than every day
4	Very frequently - daily or essentially continuously present
Severity	
1	Mild - produces little distress in the patient
2	Moderate - more disturbing to the patient but can be redirected by the caregiver
3	Severe - very disturbing to the patient and difficult to redirect
Distress	
0	No distress

### Confidentiality Statement

This document is the property of Worldwide Clinical Trials Inc. and may not be duplicated, copied, altered or removed from company without prior approval from Worldwide Quality Assurance or in compliance with Worldwide Standard Operating Procedures.

Worldwide Clinical Trials Controlled Quality Management Document		
 WORLDWIDE CLINICAL TRIALS	Sponsor:	EIP Pharma, Inc.
	Protocol Number:	EIP21-NFD-504
STATISTICAL ANALYSIS PLAN		

1	Minimal
2	Mild
3	Moderate
4	Severe
5	Very severe or extreme

NPI-12 Score of each domain = (Frequency  $\times$  severity) of the domain

Total NPI-12 Score = Sum of all 12 domain scores (frequency  $\times$  severity)

- $P_n$  = Frequency  $\times$  Severity where n = 1 to 12 and  $P_n$  = Total NPI-12 Score of each domain
- Total NPI-12 Score =  $P_1 + P_2 + \dots + P_{11} + P_{12}$

NPI-10 Score = Sum of 10 domain scores (excluding sleep, and appetite and eating change domains)

NPI-4 Score = Sum of 4 domain scores (Depression (dysphoria), Apathy, Hallucination, Agitation/aggression)

Missing data will be handled as defined in section 5.2.8.

## 5.2.20 Movement Disorder Society – Unified Parkinson’s Disease Rating Scale – Part III (MDS-UPDRS3)

The motor examination (Part III) assesses motor symptoms and signs. The total score is the sum of 33 items with scores ranging from 0-132, with higher scores meaning more severe symptoms. All items have 5 response options ranging from 0 (Normal) to 4 (Severe). Missing data will be handled as defined in section 5.2.8.

## 5.2.21 Columbia-Suicide Severity Rating Scale (C-SSRS)

The following outcomes are C-SSRS categories and have binary responses (yes / no). The categories have been re-ordered from the actual scale to facilitate the definition of composite endpoints:

Category 1	Wish to be Dead
Category 2	Non-specific Active Suicidal Thoughts
Category 3	Active Suicidal Ideation with Any Methods (Not Plan) without Intent to Act
Category 4	Active Suicidal Ideation with Some Intent to Act, without Specific Plan
Category 5	Active Suicidal Ideation with Specific Plan and Intent

### Confidentiality Statement

This document is the property of Worldwide Clinical Trials Inc. and may not be duplicated, copied, altered or removed from company without prior approval from Worldwide Quality Assurance or in compliance with Worldwide Standard Operating Procedures.

Worldwide Clinical Trials Controlled Quality Management Document		
 WORLDWIDE CLINICAL TRIALS	Sponsor:	EIP Pharma, Inc.
	Protocol Number:	EIP21-NFD-504
STATISTICAL ANALYSIS PLAN		

Category 6	Preparatory Acts or Behaviour
Category 7	Aborted Attempt
Category 8	Interrupted Attempt
Category 9	Actual Attempt (non-fatal)
Category 10	Suicide

Suicidal Ideation since baseline – A “yes” answer at any time during double-blind treatment phase to any one of the 5 suicidal ideation questions (categories 1-5) on the C-SSRS.

Suicidal Behaviour since baseline – A “yes” answer at any time during double-blind treatment phase to any one of the 5 suicidal behaviour questions (categories 6-10) on the C-SSRS.

There will be no imputation of missing data for C-SSRS.

### 5.2.22 Unscheduled Visits

Visit data will be presented using nominal times as collected in the eCRF. Both scheduled and unscheduled post-baseline visits will be tabulated. Unscheduled visits will be presented as ‘Visit x.xx’ (e.g., Visit 3.01).

### 5.2.23 Randomization Strata

The subjects are stratified by background dementia therapy as follows:

- No cholinesterase inhibitor therapy
- Cholinesterase inhibitor therapy alone
- Memantine therapy (with or without cholinesterase inhibitor therapy)

The stratification group used in the randomization (including mis-stratification) will be used for the analysis. For analysis purpose, dichotomous stratification as cholinesterase inhibitor therapy (Yes / No) will be used. Cholinesterase inhibitor therapy alone and memantine therapy (with or without cholinesterase inhibitor therapy) strata will be combined into single strata and will be considered as ‘with cholinesterase inhibitor therapy’ (cholinesterase inhibitor therapy=YES) while No cholinesterase inhibitor therapy strata will be considered as ‘without cholinesterase inhibitor therapy’ (cholinesterase inhibitor therapy=NO).

The randomization list was generated under protocol v1.0. Hence, the randomization strata text in Protocol v2.0 and SAP will not match the randomization list and IRT label. For reporting purposes, text from the SAP will be used to be consistent with the latest protocol.

QMD Ref: Worldwide-TMP-ST-054-1.0_Effective: 12Aug2022	Governing QMD: Worldwide-SOP-ST-026
Confidentiality Statement	
This document is the property of Worldwide Clinical Trials Inc. and may not be duplicated, copied, altered or removed from company without prior approval from Worldwide Quality Assurance or in compliance with Worldwide Standard Operating Procedures.	

Worldwide Clinical Trials Controlled Quality Management Document		
 WORLDWIDE CLINICAL TRIALS	Sponsor:	EIP Pharma, Inc.
	Protocol Number:	EIP21-NFD-504
STATISTICAL ANALYSIS PLAN		

### 5.3 Conventions

All data listings, summaries, figures and statistical analyses will be generated using SAS version 9.4 or higher.

Summaries will be presented by treatment group or overall. Subjects will be summarized under same treatment group in both double-blind and open-label extension phase. Treatment group labels will be displayed as follows:

Neflamapimod	Placebo
(40mg TID)	(N=XX)
(N=XX)	

Listings will be sorted in the following order treatment group, subject, parameter, and visit unless otherwise stated. All data will be listed, subjects who were not randomized will be displayed after the randomized treatment / sequence groups. Any safety/efficacy data collected during screening for the subjects who failed screening will not be included in the TLFs.

Continuous variables will be summarized by the number of non-missing observations, mean, median, standard deviation, and minimum and maximum.

Categorical variables will be summarized by presenting the frequency and percent. Percentages will be based on the number of subjects in the column header unless otherwise specified in the footnote. For each variable, all categories will be shown. Zero frequencies (but not the percent) within a category will be presented.

Means, medians and percentiles will be displayed to one more decimal place than the data, dispersion statistics (e.g., standard deviation) will have two more decimal places, and the minimum and maximum will be displayed to the same number of decimal places as reported in the raw data. If the reported/derived data contains more than 3 decimals, they will be rounded off to three decimal places before calculating the summaries. Percentages will be displayed with one decimal place.

Estimates and confidence intervals will be displayed to one more decimal place than the data, if estimate values are very small (i.e., <0.005) then estimates will be presented with decimals up to 2 significant digits; standard error will be displayed to two more decimal places than the data.

P- Values will be quoted to 4 decimal places consistent with SAS PVALUEw.d format set to PVALUE6.4. P-values < 0.0001 will be presented as p<0.0001.

### 5.4 Subject Disposition

Subject disposition will be summarized as follows:

QMD Ref: Worldwide-TMP-ST-054-1.0 Effective: 12Aug2022	Governing QMD: Worldwide-SOP-ST-026
Confidentiality Statement  This document is the property of Worldwide Clinical Trials Inc. and may not be duplicated, copied, altered or removed from company without prior approval from Worldwide Quality Assurance or in compliance with Worldwide Standard Operating Procedures.	

Worldwide Clinical Trials Controlled Quality Management Document		
 WORLDWIDE CLINICAL TRIALS	Sponsor:	EIP Pharma, Inc.
	Protocol Number:	EIP21-NFD-504
STATISTICAL ANALYSIS PLAN		

- The number of subjects who entered the study, were randomized, and who are in each analysis set will be summarized by treatment group and overall. Separate summaries will be provided for the double-blind treatment phase and open-label extension phase.
- The number and percentage of subjects who completed the double-blind treatment phase, the open-label extension phase, overall study and who terminated early, along with reasons for early termination (ET), will be presented for the Full Analysis Set. Summaries will be presented separately for the double-blind treatment phase and the open-label extension phase.
- The number of subjects who failed screening and the reasons for failure will be tabulated for the Screened Set.
- The number and percentage of subjects failing each eligibility criteria will be tabulated for the Screened Set.
- The initial recruitment to double-blind treatment phase will be summarized by country and site for the double-blind treatment phase and open-label extension phase for the Full Analysis Set.
- The number of subjects present at each scheduled visit will be summarized by treatment group for the double-blind treatment phase and open-label extension phase for Full Analysis Set.

All subject disposition data and screen failures will be listed.

## 5.5 Protocol Deviations

Protocol deviations will be summarized for the double-blind treatment phase and open-label extension phase separately for the Full Analysis Set. The summary will be provided by classification (Major, Minor) and description listed under 'Protocol deviation description' in the latest version of Protocol Deviation Handling Plan. A listing of protocol deviations will be provided within Appendix 16.2 of the CSR.

## 5.6 Demographics and Baseline Comparability

The comparability of treatment groups with respect to subject demographics and baseline characteristics will be assessed in a descriptive manner, but no formal statistical testing will be performed.

Standard continuous or categorical variable summaries will be presented by randomized treatment group for the following variables based on the Safety Analysis Set and Full Analysis Set separately for double-blind treatment phase.

- Demographic data
  - Age at informed consent (years)
  - Sex

QMD Ref: Worldwide-TMP-ST-054-1.0_Effective: 12Aug2022	Governing QMD: Worldwide-SOP-ST-026
Confidentiality Statement	

This document is the property of Worldwide Clinical Trials Inc. and may not be duplicated, copied, altered or removed from company without prior approval from Worldwide Quality Assurance or in compliance with Worldwide Standard Operating Procedures.

Worldwide Clinical Trials Controlled Quality Management Document		
 WORLDWIDE CLINICAL TRIALS	Sponsor:	EIP Pharma, Inc.
	Protocol Number:	EIP21-NFD-504
STATISTICAL ANALYSIS PLAN		

- Fertility status
- Ethnicity
- Race
- Weight at screening (kg)
- Baseline characteristics
  - Background dementia therapy (Randomization Strata)
  - MMSE Total Score
  - Subject's DLB diagnosis confirmed with the presence of dementia plus 2 or more core clinical features
  - DaTscan result (in case of missing historic DaTscan, screening DaTscan will be used)
  - Presence of historical diagnosis
  - Core clinical features
  - Presence of evidence of other neurodegenerative disease

## 5.7 Medical History

Separate tabulations of previous and ongoing conditions will be presented by randomized treatment group and overall, for the Safety Analysis Set. Conditions will be presented by Medical Dictionary of Regulated Activities (MedDRA) primary system organ class and preferred term. MedDRA version 26.1 or higher will be used for coding purposes.

## 5.8 Prior and Concomitant Medications

Separate tabulations will be produced for prior and concomitant medications presented by randomized treatment group and overall, for the Safety Analysis Set. Prior medications are defined as medications that ended before the date of the first dose of study drug. Concomitant medications are defined as medications that ended or are ongoing on or after the date of the first dose of study drug.

The following rules will be used in the analysis of concomitant medications:

- Concomitant medications will be counted in the double-blind treatment phase if the end date is on or before the end of double-blind treatment phase (Follow-Up: Day 118 to Last dose+14 days).
- Concomitant medications starting after the end of the double-blind treatment phase will be counted in the open-label extension phase.
- Concomitant medications starting in or before the double-blind treatment phase and ongoing in the open-label extension phase will be counted in both treatment phases for period-wise summaries and will be counted once for the overall study summary.

QMD Ref: Worldwide-TMP-ST-054-1.0_Effective: 12Aug2022	Governing QMD: Worldwide-SOP-ST-026
Confidentiality Statement	

This document is the property of Worldwide Clinical Trials Inc. and may not be duplicated, copied, altered or removed from company without prior approval from Worldwide Quality Assurance or in compliance with Worldwide Standard Operating Procedures.

Worldwide Clinical Trials Controlled Quality Management Document		
 WORLDWIDE CLINICAL TRIALS	Sponsor:	EIP Pharma, Inc.
	Protocol Number:	EIP21-NFD-504
STATISTICAL ANALYSIS PLAN		

All the above summaries will be presented using Anatomic Therapeutic Chemical (ATC) Level 2 and preferred term coded using the WHO Drug (B3 Global) dictionary, version September 2023 or higher.

All prior and concomitant medications will be listed. A separate listing will be provided for cholinesterase inhibitors and memantine therapy.

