#### **Partial or missing stop date will be imputed as follows:**

- If the stop date is completely missing and the event has resolved, or the subject has stopped taking the concomitant medication, the stop date will be imputed as the date of the subject's last clinic visit in the study.
- If only the year is known, the stop date will be imputed as "31-Dec" of that year or as the date of the subject's last clinic visit in the study if in the same year.

QMD Ref: Worldwide-TMP-ST-054-1.0_Effective: 12Aug2022	Governing QMD: Worldwide-SOP-ST-026
Confidentiality Statement	
This document is the property of Worldwide Clinical Trials Inc. and may not be duplicated, copied, altered or removed from company without prior approval from Worldwide Quality Assurance or in compliance with Worldwide Standard Operating Procedures.	

Worldwide Clinical Trials Controlled Quality Management Document		
 WORLDWIDE CLINICAL TRIALS	Sponsor:	EIP Pharma, Inc.
	Protocol Number:	EIP21-NFD-504
STATISTICAL ANALYSIS PLAN		

- If the month and year are known, the stop date will be imputed as the last day of that month unless the stop date corresponds to the same month as the subject's last clinic visit in which case the date of subject's last clinic visit in the study will be used instead.

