### 5.2.11 Adverse Events

A treatment-emergent Adverse Event (TEAE) is defined as one that started, or worsened in severity or seriousness, following the first dose of study drug. An AE with onset prior to the start of administration of the first dose of study drug, or when the stop date is before the start of the administration of the first dose of study drug, or when the study drug was not started, will be considered as pre study. In case the onset date is on the same day as the first dose of study drug

QMD Ref: Worldwide-TMP-ST-054-1.0_Effective: 12Aug2022	Governing QMD: Worldwide-SOP-ST-026
Confidentiality Statement	
This document is the property of Worldwide Clinical Trials Inc. and may not be duplicated, copied, altered or removed from company without prior approval from Worldwide Quality Assurance or in compliance with Worldwide Standard Operating Procedures.	

Worldwide Clinical Trials Controlled Quality Management Document		
 WORLDWIDE CLINICAL TRIALS	Sponsor:	EIP Pharma, Inc.
	Protocol Number:	EIP21-NFD-504
STATISTICAL ANALYSIS PLAN		

and either the time of first dose or time of AE onset is missing, then AE is considered treatment-emergent.

TEAEs starting after first dose of study drug in the double-blind treatment phase and before the first dose of study drug in the open-label extension phase will be summarized under the Double-Blind summary. TEAEs starting after first dose of study drug in open-label extension phase will be summarized under the open-label extension phase.

Maximum severity (Severe) will be assumed for an AE with missing severity.

A treatment-related AE is defined as an AE as being possibly related or related to the study drug. If an AE has missing relationship it is assumed to be related to the study drug for analysis purposes.

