## 6 INTERIM ANALYSIS

No interim analysis is planned. The primary analyses will be performed after the blinded treatment phase of 16 weeks. Subjects may go on to a long term open-label extension and a final analysis will be performed with the additional long-term data.

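### SAP section 5.8 assigns concomitant drugs to phases by end date, so drugs ongoing at exit in patients who never enter the open-label extension are counted in neither phase table (minor; descriptive tables only)

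*SAP*

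**What the plan says.** Section 5.8 first defines the class: "Concomitant medications are defined as medications that ended or are ongoing on or after the date of the first dose of study drug". It then gives three rules for assigning such a drug to a phase.

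- Double-blind: "Concomitant medications will be counted in the double-blind treatment phase if the end date is on or before the end of double-blind treatment phase". The end of the phase is given in brackets as "Follow-Up: Day 118 to Last dose+14 days".
- OLE: "Concomitant medications starting after the end of the double-blind treatment phase will be counted in the open-label extension phase".
- Both: "Concomitant medications starting in or before the double-blind treatment phase and ongoing in the open-label extension phase will be counted in both treatment phases", with a single count in an overall summary.

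Three other places bear on these rules.

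- Section 5.2.7.1 imputes a wholly missing stop date only for a drug that was stopped: "If the stop date is completely missing and the event has resolved, or the subject has stopped taking the concomitant medication".
- Section 6 makes OLE entry optional: "Subjects may go on to a long term open-label extension".
- Section 5.2.11 divides adverse events at a different point. Those starting after the first double-blind dose and "before the first dose of study drug in the open-label extension phase will be summarized under the Double-Blind summary".

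Section 10 lists the by-phase tables as 14.3.8.1a and 14.3.8.1b, both on the Safety Analysis Set. It lists no overall-study medication table.

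**The concern.** A phase table of concomitant drugs should show what patients took during that phase. The double-blind rule instead asks when the drug ended. A drug with no end date can reach the double-blind table only through the third rule, and that rule needs an OLE for the drug to continue into. A patient without an OLE has no such route.

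What is at stake is the accuracy of two descriptive safety tables. Section 5.3 bases percentages on the column-header count, so a patient whose ongoing drug is omitted still counts in the denominator and appears not to have taken it.

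A second, conditional problem is the boundary. Fourteen days after the last dose may fall inside the OLE of a patient who rolls over, and section 5.8 makes no exception for such patients. Adverse events are cut at the first OLE dose, so an event and the drug given for it could land in different phases.

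**Working it through.** The plan states no figure to reproduce. The check applies the three rules literally to test records.

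**Inputs.** The rules and the boundary come from section 5.8, the stop-date imputation from section 5.2.7.1 and the adverse-event cut from section 5.2.11. Assumed for illustration: last double-blind dose on Day 112, so the phase ends on Day 112 + 14 = Day 126; for an early withdrawal, last dose on Day 30, so it ends on Day 30 + 14 = Day 44.

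**Step 1. Patient who never enters the OLE.**

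| Drug | End date by boundary? | Starts after boundary? | Continues into OLE? | Phase |
|---|---|---|---|---|
| Chronic, ongoing at exit | no end date | no | no OLE | none |
| Started Day 50, ongoing | no end date | no | no OLE | none |
| Started Day 50, ended Day 200 | 200 > 126, no | no | no OLE | none |
| Started Day 50, ended Day 60 | 60 ≤ 126, yes | no | no OLE | double-blind |
| Chronic, ongoing; last dose Day 30 | no end date | no | no OLE | none |

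For ongoing drugs the result does not depend on the assumed days: with no end date the first rule fails at any boundary. Section 5.2.7.1 does not supply a date, because the drug has not been stopped. All five drugs meet the section 5.8 definition of concomitant.

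**Step 2. Patient who rolls over (conditional).** The SAP does not state the gap between last double-blind dose and first OLE dose, so it is varied. With gap g days, the first OLE day is 112 + g. The OLE days on or before Day 126 number 126 − (112 + g) + 1 = 15 − g, and never less than 0.

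| Gap (days) | OLE days inside the double-blind boundary |
|---|---|
| 1 | 14 |
| 4 | 11 |
| 7 | 8 |
| 14 | 1 |
| 15 | 0 |

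A drug started on one of those days is counted as double-blind only if it also stops by Day 126. If it continues past Day 126, the third rule counts it in both phases. Under section 5.2.11 an adverse event starting after the first OLE dose is counted in the OLE only.

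**The case against.** The strongest reply is that this is a drafting omission with little consequence. The records are not lost: listing 16.2.4.4 holds all prior and concomitant drugs, and listing 16.2.4.5 holds cholinesterase inhibitors and memantine. Background dementia therapy is also summarized by randomized group in the baseline tables, which do not use the phase rule. No efficacy model reads these medication tables. All of that stands and keeps the point minor. It does not make the counts right. Nor is it safe to expect programmers to do the sensible thing: the tables are checked by independent programming against a written rule, and for these patients the rule gives a definite wrong answer.

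On the boundary, the reply is stronger. The follow-up window repeats one from Table 1 of section 5.2.4, which maps early-withdrawal visits. The SAP does not say that patients who roll over have that window, nor how long the gap is. That part can therefore be stated only as conditional.

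A reader might go further in four ways that the document does not support.

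- **A share of patients affected.** Subtracting the 149 in the OLE from the planned 160 gives 11, or 7%. This sets an actual count against an approximate plan; the number randomized is not given.
- **A share of drugs misplaced.** Fourteen of 224 OLE days is 6%, but that is a share of days, not of drugs.
- **Damage to the estimand.** Section 2.3 uses all observed data regardless of prohibited medication, and protocol deviations are summarized separately, so no estimate depends on these tables.
- **Last dose meaning the last OLE dose.** Tables 1 and 2 of section 5.2.4 use the same phrase separately for each phase, so that reading is strained.

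**Conclusion.** The point holds as a minor error of specification. For patients who leave without entering the OLE, any concomitant drug ongoing at exit, or ending after last dose + 14 days, is omitted from both by-phase tables. For ongoing drugs this follows from the text alone. For drugs ending later it rests on taking last dose + 14 days as the end of the double-blind phase, as section 5.8 indicates. The number of patients and drugs cannot be derived from the document.

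The inconsistency with the adverse-event split holds only on two assumptions: that OLE dosing begins within 14 days of the last double-blind dose, and that the follow-up boundary also applies to patients who roll over. Even then, only drugs that both start and stop inside the overlap are missing from the OLE table.

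The effect is confined to Tables 14.3.8.1a and 14.3.8.1b.

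**What to change.** Replace the three bullets of section 5.8 with an overlap rule that uses the adverse-event cut:

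- **Double-blind:** start date before the first OLE dose (or, if there is no OLE, on or before last dose + 14 days), and either an end date on or after the first double-blind dose or the drug ongoing.
- **OLE:** only patients dosed in the OLE, with an end date on or after the first OLE dose or the drug ongoing.
- **Both:** a drug meeting both conditions is counted in both phases.

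Under this rule all five test drugs in step 1 fall in the double-blind table, and a drug started after the first OLE dose falls in the OLE table only, whatever the gap.

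The database is already locked and unblinded, so the change belongs in the post-database-lock addendum that section 5 provides for. It needs no new data: one changed flag derivation and a re-run of the two tables.
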